4.5 Analysis Centers

Prior to database lock, a review of the blinded data will be performed to determine the size of each center. If there are centers with a small number of randomized subjects, then these centers will be pooled in order for analyses to be carried out. The process of combining centers will be based on the ITT Set, and same pooling will be repeated for the mITT Set and the PP Set.

[figure not shown]
A small center is defined as a center which randomizes less than 15 subjects. First, centers will be sorted by geographic region, country, number of randomized subjects (descending order) and center number (ascending order). Pooling will start with combining the largest of the set of small centers of a country with the smallest center within the same country (if applicable) or within the same geographic region. If there is a further need to combine data (the size of the pooled centers includes less than 15

subjects), the next smallest center will be combined with the next largest of the small centers, until the criterion of a minimum of 15 subjects is met. The process will continue until all pooled centers have a minimum of 15 subjects within the same geographic region. Any remaining small centers of a country/geographic region will be pooled with the last pooled center within the same country/geographic region. The pooled centers and the remaining original unpooled clinical centers will be referred to as ‘analysis centers’ and will be used as stratification factor in the statistical analyses.

If at the start of pooling any geographic region has less than 15 subjects in the ITT Set in total, then centers will be added to the list of small centers in another geographic region and then combined as above. This decision will be documented in Clinical Study Report.

4.6 Adjustments for Covariates

CCI

4.7 Handling of Missing Data

Missing data of the following dichotomous efficacy endpoints:

- Proportion of subjects with an improvement of WI NRS ≥ 4 from baseline at Week 12
- Proportion of subjects with an improvement of WI NRS ≥ 3 from baseline at Week 12
- Proportion of subjects with an improvement of WI NRS ≥ 4 from baseline at Week 4

- Proportion of subjects with an improvement of SD NRS ≥ 4 from baseline at Week 12
- Proportion of subjects with an improvement of WI NRS ≥ 3 from baseline at Week 4
- Proportion of subjects with an improvement of SD NRS ≥ 4 from baseline at Week 4
- Proportion of subjects with an improvement of WI NRS ≥ 4 from baseline at Week 1

will be imputed using multiple imputations (MI) under missing at random (MAR) assumption for the primary/main analysis. Dichotomous endpoints will be calculated from the underlying imputed variable (i.e., weekly averages of WI NRS and SD NRS, as applicable).

For the sensitivity analyses of the primary endpoint, missing data will be imputed using a copy reference (CR) approach under missing not at random (MNAR) assumption (dichotomous endpoints will be calculated from the underlying imputed variable) and as “Non-responder”; moreover a Tipping Point analysis under MNAR assumption will be carried out (see [Appendix C](#) for details about Multiple Imputation and Tipping Point analysis).

[figure not shown]
Multiple imputation will be based on data collected up to Week 12. A further sensitivity analysis based on MI using all data collected up to Week 20 may be performed.

Similarly, sensitivity analyses will be performed by imputing missing data using a CR approach under MNAR assumption and as “Non-responder” for the key secondary efficacy endpoints based on WI NRS and SD NRS.

[figure not shown]
Subjects who took rescue therapies or discontinued treatment due to lack of efficacy or AE/death related to study drug will be considered as treatment failures in the endpoints defined for Estimands 1 to 6 (see section [5](#)). The values of the variable of interest collected after the use of rescue therapies or treatment discontinuation due to lack of efficacy or AE/death related to study drug will be set to the worst possible value and subject’s binary response will be imputed as “Non-responder” prior to conducting the MI and Tipping Point analysis.

Missing data of the following dichotomous efficacy endpoint:

CCI

A large black rectangular box redacting content.

CCI

will be imputed using MI under MAR assumption for the main analysis; changes and percent changes from baseline will be calculated from the imputed variables (i.e. questionnaires' scores and weekly averages of WI NRS and CCI). Subjects who took rescue therapies or discontinued treatment due to lack of efficacy or AE/death related to study drug will be considered as treatment failures. The values of the variable of interest collected after the use of rescue therapies or treatment discontinuation due to lack of efficacy or AE/death related to study drug will be set to the worst possible value prior to conducting the MI. See [Appendix C](#) for details of the multiple imputation process.

4.8 Use of an Efficacy Subset of Subjects

The classification of the protocol deviations and the exclusion of subjects from the Per Protocol (PP) Set will be determined prior to breaking the study blind (see section [6.2](#)).

The analysis on the PP Set will allow evaluating the impact of major protocol deviations on the estimation of the treatment effect.

4.9 Examination of Subgroups

Descriptive summaries and analyses for primary and key secondary efficacy endpoints will be produced for the following subgroups:

- Age group (18 to 45; >45 to 65; >65 to 80; >80)
- Sex (Male, Female)
- Race group (White, Black, Asian, Other)
- Region (US; Excl-US)
- Severity of pruritus at baseline (5 to 7; >7 to 10)
- Duration of pruritus at baseline (\leq 3 months; >3 to 12 months; >12 months)
- Duration of hemodialysis at baseline (\leq 1 year; >1 year to 3 years; >3 years)
- Subjects with or without prior or concomitant systemic anti-pruritus treatment

Prior or concomitant systemic anti-pruritus treatments will be identified based on a list provided by Galderma medical experts.

4.10 Analysis Visit Windows

All by-visit summaries and analyses will use the analysis visits. Scheduled, unscheduled and early termination visits will be windowed based on the following analysis visit windows which are based on study day. Details of the analysis visit window of efficacy and safety assessments/measurements collected during clinical visits are in the table below.

Table 3 Analysis visit windows for efficacy and safety assessments or measurements collected during clinical visits

Analysis Visit	Target Study Day	CCI	Analysis Windows for ACT, PEF testing, Respiratory exam, Full physical examination, Vital signs, Blood samples for hematology and biochemistry, Urinalysis, Pregnancy test	Analysis Windows for 12-lead ECG, Pre-Dialysis and Post-Dialysis Weight	Analysis Windows for Height, Blood sample for virology and TB test, FSH	CCI
Baseline	1		≤ 1	≤ 1	≤ 1	
Week 4	29		2 to 42	NA	NA	
Week 8	57		43 to 70	NA	NA	
Week 12	85		71 to 113	≥ 2	NA	
Week 20	141		≥ 114	NA	NA	

If multiple assessments/measurements are taken within the same window, then all assessments will be listed, and the following rules will be applied for determining the values to be used for the summaries and analyses:

- Efficacy assessments: the assessment/measurement closer to the target study day will be used for the summaries and analyses. If there are multiple measurements with same difference from target day, the latest assessment will be used for the summaries and analyses.
- Safety assessments, excluding clinical laboratory tests: the assessment/measurement closer to the target study day will be used for the summaries and analyses. If there are multiple measurements with same difference from target day, the latest assessment will be used for the summaries and analyses.

- Clinical laboratory tests: the latest assessment will be used for the summaries and analyses.

CCI

Analysis visits of ePRO data will be defined depending on the data collection as below.

For the evening assessments of WI NRS, the daily data collected up to Week 20 will be classified into analysis visits considering the data during the 7 days immediately preceding the target study day of analysis visit. Similarly, for the morning assessment of WI NRS (if the WI NRS assessment in the evening is missed, the subjects are allowed to complete the assessment the following morning) and SD NRS, the 7 days data up to the target study day will be classified into analysis visit. Details of the analysis visit window of ePRO data are in the table below.

Table 4 Analysis Visit Windows for calculation of Weekly Average of WI NRS and SD NRS

Analysis Visit	Target Study Day	Analysis Windows for WI NRS Evening Assessments	Analysis Windows for WI NRS Following Morning Assessments *	Analysis Windows for SD NRS Morning Assessments
Baseline ^a	1	-7 to -1	-6 to 1 before dosing	-6 to 1 before dosing
Week 1	8	1 to 7	2 to 8	2 to 8
Week 2	15	8 to 14	9 to 15	9 to 15
Week 3	22	15 to 21	16 to 22	16 to 22
Week 4	29	22 to 28	23 to 29	23 to 29
Week 5	36	29 to 35	30 to 36	30 to 36
Week 6	43	36 to 42	37 to 43	37 to 43
Week 7	50	43 to 49	44 to 50	44 to 50
Week 8	57	50 to 56	51 to 57	51 to 57
Week 9	64	57 to 63	58 to 64	58 to 64
Week 10	71	64 to 70	65 to 71	65 to 71
Week 11	78	71 to 77	72 to 78	72 to 78
Week 12 ^b	85	78 to 84	79 to 85	79 to 85
Week 13	92	85 to 91	86 to 92	86 to 92
Week 14	99	92 to 98	93 to 99	93 to 99
Week 15	106	99 to 105	100 to 106	100 to 106
Week 16	113	106 to 112	107 to 113	107 to 113
Week 17	120	113 to 119	114 to 120	114 to 120
Week 18	127	120 to 126	121 to 127	121 to 127

Analysis Visit	Target Study Day	Analysis Windows for WI NRS Evening Assessments	Analysis Windows for WI NRS Following Morning Assessments *	Analysis Windows for SD NRS Morning Assessments
Week 19	134	127 to 133	128 to 134	128 to 134
Week 20	141	134 to 140	135 to 141	135 to 141

*: If the WI NRS assessment in the evening is missed, the subjects are allowed to complete the assessment the following morning.

- a: For baseline weekly average, if fewer than 4 daily WI NRS/SD NRS scores for the 7-day period are available, the interval lower bound will be extended up to 7 additional days, one day at a time, until 4 daily WI NRS/SD NRS scores are available. If after the interval extension fewer than 4 daily WI NRS/SD NRS scores are available, the baseline weekly average WI NRS/SD NRS will be considered missing.
- b: For week 12 weekly average, if fewer than 4 daily WI NRS/SD NRS scores for the 7-day period are available, the interval upper bound will be extended for 5 additional days, one day at a time, until 4 daily WI NRS/SD NRS scores are available. If after extending the upper bound fewer than 4 daily WI NRS/SD NRS scores available, the interval lower bound will be extended for 5 additional days, one day at a time, until 4 daily scores are available. If after the interval extension fewer than 4 daily WI NRS/SD NRS scores are available, the week 12 weekly average WI NRS/SD NRS will be considered missing.

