13.2.2 Unscheduled Visit

The subject should be reminded to adhere to the study schedule. Unscheduled visits are defined as visits to repeat testing for abnormal laboratory results, for follow-up of AEs, or to conduct efficacy assessments for subjects requiring rescue medication between regularly scheduled study visits. Visits occurring outside of the visit window are not considered unscheduled visits.

CCI

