16.4 Clinical Laboratory Evaluation

The hematology laboratory analyses, biochemistry laboratory analyses, and urinalyses will be performed at a central laboratory. Reference ranges will be supplied by the central laboratory and used by the investigator to assess the laboratory data for clinical significance and pathological changes.

The investigator or medically qualified sub-investigator must review and evaluate laboratory values for each subject in a timely manner. Study centers should refer to the current version of the laboratory manual for laboratory values outside of normal limits. For each out-of-range laboratory result, the investigator or designee will evaluate whether he/she considers it to be CS, defined as meeting at least 1 of the following conditions:

- The abnormality suggests a disease and/or organ toxicity, or
- The abnormality is of a degree that requires additional active management (e.g., discontinuation of the drug, close observation, more frequent follow-up assessments, or further diagnostic investigation).

If the investigator observes a CS laboratory result that meets the criteria for an adverse event or at the investigator's discretion, the test will be repeated as soon as possible, and the subject will be monitored until the value returns to normal and/or an adequate explanation for the abnormality is found.

Investigators will also be allowed to repeat specific laboratory test(s) or procedure(s) where the investigator suspects an inaccuracy or false result and that may impact the safety of the subject or the interpretation of the trial results; only after discussion with medical monitor.

All CS out-of-range laboratory values at the screening visit will be recorded in the medical history form (report a diagnosis rather than the laboratory value whenever possible). All CS out-of-range laboratory values after the screening visit are to be reported as an AE if this abnormality was not present at the screening visit or is assessed as having worsened since the screening visit (i.e., changed by a clinically significantly extent from the screening visit). Whenever possible, the investigator should provide a diagnosis of an AE when reporting the abnormal laboratory value.

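### The rule of keeping the latest laboratory result in each analysis window lets retests prompted by abnormal values replace the scheduled value in by-visit laboratory rows

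*SAP*

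**What the plan says.** SAP section 4.10 assigns results to analysis visits by study day: "Scheduled, unscheduled and early termination visits will be windowed based on the following analysis visit windows which are based on study day". For hematology, biochemistry and urinalysis, Table 3 sets Week 4 as Days 2 to 42, Week 8 as Days 43 to 70, Week 12 as Days 71 to 113, and Week 20 as Day 114 onwards.

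When several results fall in one window, two rules apply to safety data:

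- Non-laboratory measures: "Safety assessments, excluding clinical laboratory tests: the assessment/measurement closer to the target study day will be used for the summaries and analyses". The later result breaks a tie.
- Laboratory measures: "Clinical laboratory tests: the latest assessment will be used for the summaries and analyses".

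No reason is given for the difference.

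The protocol explains where additional laboratory results come from. Section 13.2.2: "Unscheduled visits are defined as visits to repeat testing for abnormal laboratory results", among other purposes. Section 16.4 concerns "a CS laboratory result that meets the criteria for an adverse event or at the investigator's discretion" and says that "the test will be repeated as soon as possible", with the subject "monitored until the value returns to normal and/or an adequate explanation for the abnormality is found". Section 16.4 also permits a repeat when the investigator suspects a wrong result, after discussion with the medical monitor.

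SAP section 12.2 uses the analysis visits for observed values, changes from baseline, two sets of shift tables (reference range; clinical significance) at Weeks 4, 8, 12 and 20, and boxplots of liver tests and CPK over visits. The same section adds worst and last post-baseline results, and it determines PCSVs from every post-baseline measurement and tabulates them by visit.

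**The concern.** A second laboratory result in a window is usually not a random extra draw. It tends to exist because the first result was abnormal, and it comes after that result. Keeping the latest value therefore makes the choice of which result to show depend on what the scheduled result was. Subjects with unremarkable scheduled values keep them, while subjects with abnormal ones are often represented by their retest.

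Three things follow for the visit rows:

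- A transient abnormality can disappear from the visit at which it occurred.
- Timing can be misattributed. Protocol section 13 has safety blood drawn before dialysis and the injection given after it. A Week 4 value taken on Days 30 to 42, or a Week 8 value taken on Days 58 to 70, may therefore follow the injection that the scheduled sample preceded.
- Tables can contradict each other. A subject can count as a PCSV at Week 4, where all measurements are used, while the Week 4 shift row shows a normal result.

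**Working it through.** The plan states no figure on this point, so there is none to reproduce. The check applies the Table 3 windows to the competing selection rules.

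**How late a retest can be and still replace the scheduled value** (window end minus visit day; range from the allowed visit windows of ±3 days at Weeks 4 and 8 and ±5 days at Week 12):

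| Visit | On target day | Range |
|---|---|---|
| Week 4 | 42 − 29 = 13 days | 10 to 16 |
| Week 8 | 70 − 57 = 13 days | 10 to 16 |
| Week 12 | 113 − 85 = 28 days | 23 to 33 |
| Week 20 | no upper limit | – |

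A prompt repeat would usually fall inside these limits.

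**What each rule shows at Week 4** (assumed values, multiples of the upper limit of normal, scheduled draw 4.0 on Day 29):

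| Retest | Latest in window | Closest to Day 29 | Worst post-baseline |
|---|---|---|---|
| 0.9 on Day 36 | 0.9 | 4.0 | 4.0 |
| 6.0 on Day 36 | 6.0 | 4.0 | 6.0 |
| 0.9 on Day 44 (outside window) | 4.0 | 4.0 | 4.0 |

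The first row shows the problem. The second shows that the direction can reverse. The third shows that a retest outside the window replaces nothing at Week 4.

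**Would the closest-to-target rule be enough?** Not when the scheduled draw is early:

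- Scheduled Day 26, retest Day 32: |26 − 29| = 3 and |32 − 29| = 3. The tie goes to the later result, the retest.
- Scheduled Day 26, retest Day 30: 3 days v 1 day, so the retest is kept.
- Scheduled Day 80, retest Day 87, target Day 85: 5 days v 2 days, so the retest is kept.

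**Size, on assumed counts.** The documents give no abnormality rates. Assume that 6 of 84 nemolizumab and 2 of 84 placebo subjects have a clinically significant scheduled value at a visit, and that a fraction f in each arm is replaced by a retest that is no longer clinically significant. The proportion shown is (1 − f) × the scheduled proportion.

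- f = 0: 6/84 = 7.1% v 2/84 = 2.4%; difference 4/84 = 4.8 points.
- f = 1/2: 3/84 = 3.6% v 1/84 = 1.2%; difference 2/84 = 2.4 points.
- f = 1, the outer bound: 0% v 0%.

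For any common f below 1, the 3:1 ratio is unchanged and the absolute difference shrinks in proportion.

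**The case against.** **The abnormal value remains visible.** This stands. SAP section 12.2 puts worst post-baseline results into the same summaries and shift tables. It also plans maximum-value boxplots, individual plots of liver tests and CPK, an eDISH plot, and separate listings of abnormal values and PCSVs. Under protocol section 16.4, clinically significant values that are new or worse since screening are reported as adverse events. Laboratory summaries are descriptive, so no test depends on the rule. However, a worst-value row does not show when the abnormality occurred, which is what the visit rows are for.

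**A retest can be the better value.** This also stands in part. If the first result is suspected to be false, the repeat should replace it. But the SAP rule is not limited to that case.

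**Stronger readings the documents do not support.**

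- A reader might infer that sites must retest every clinically significant result until it is normal, so that the latest value is a recovered one by design. Section 16.4 is narrower. The repeat is triggered by a result that meets adverse event criteria or by investigator discretion, and monitoring may end with an adequate explanation instead of a normal value.
- A reader might infer that all by-visit laboratory tables are affected. The by-visit PCSV table uses every measurement and is not.
- A reader might infer that a difference between arms would vanish. With the assumed counts, leaving one abnormal subject per arm means replacing 5 of 6 (83%) on nemolizumab but 1 of 2 (50%) on placebo. Nothing in the documents supports such unequal replacement.

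**Conclusion.** The point holds for a limited set of outputs: by-visit descriptive statistics, by-visit shift rows and by-visit boxplots of laboratory data. There, a retest in the same window replaces the scheduled result, and retests are mainly prompted by abnormality. The visit rows can therefore understate transient abnormalities, mix pre- and post-injection samples, and disagree with the by-visit PCSV table.

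The effect on the overall safety picture is modest because the worst-value, PCSV, adverse event and listing outputs retain the abnormal result. Its size cannot be fixed from the documents. It depends on how many results are retested within the window and how many of those recover. The illustration of 7.1% v 2.4% shown as 3.6% v 1.2% rests on assumed counts, equal replacement of half in each arm, and retests that recover. Efficacy conclusions are untouched. This is a cheap improvement, not a flaw that threatens the trial.

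**What to change.** Replace the laboratory bullet in SAP section 4.10 with a rule for post-baseline by-visit laboratory rows:

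- The scheduled-visit sample takes precedence.
- An unscheduled result, the one closest to the target day, is used only if the window holds no valid scheduled sample or the scheduled sample is documented as inaccurate or invalid.

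Adopting the closest-to-target rule alone would not be enough, given the early-draw cases above.

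Leave unchanged the baseline definition (last value before the first injection) and the planned worst-post-baseline, last-post-baseline and PCSV outputs. Site retesting practice is not affected.

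The cost is one SAP sentence, one programming rule and a check to identify invalid scheduled samples. No additional data are needed.

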4.11 Analysis Sets

A summary of the analysis sets including the number and percentage of subjects for the following categories: subjects in the ITT Set, subjects in the mITT Set, subjects in the PP Set, subjects in the Safety Set, and subjects in the **CCI** [REDACTED] will be presented. All percentages will be based on the number of subjects randomized. A corresponding listing will be displayed.

4.11.1 Intent-to-treat (ITT) Set

The Intent-to-treat (ITT) Set consist of all randomized subjects. The ITT Set will be the primary set for all efficacy analysis. Subjects will be summarized and analyzed according to their randomized treatment group.

4.11.2 Modified Intent-to-Treat (mITT) Set

The Modified Intent-to-treat (mITT) Set consist of all ITT subjects who receive at least one dose of study drug and have at least one post baseline assessment of primary efficacy variable. The mITT Set will be used for the supplementary analysis of the primary endpoint. Subjects will be summarized and analyzed according to their randomized treatment group.

[figure not shown]
4.11.3 Per Protocol (PP) Set

The Per Protocol (PP) Set include all randomized subjects who receive all scheduled doses of study drug and have Baseline and Week 12 assessments of WI NRS and with no major deviation that could impact efficacy. The PP Set will be used for the supplementary analysis of the primary endpoint. Subjects will be summarized and analyzed according to their randomized treatment group.

4.11.4 Safety Set

The Safety Set includes all randomized subjects who receive at least one dose of study drug. All safety data will be summarized based on the Safety Set. Subjects will be summarized according to their actual treatment group.

CC1

5 Estimands

The estimands for primary and key secondary endpoints provide precise descriptions of the treatment effect reflecting the clinical questions posed by the trial objectives. They summarize at a population level what the outcomes would be in the same patients under different treatment conditions being compared.

The intercurrent events are events occurring after treatment initiation that affect either the interpretation or the existence of the measurements associated with the clinical question of interest. It is necessary to address intercurrent events when describing the clinical question of interest in order to precisely define the treatment effect that is to be estimated.

The intercurrent events identified for this study and the estimands for primary and key secondary endpoints are defined in the following tables.

Table 5 List of Intercurrent Events

Intercurrent Event	Strategy to Deal With Intercurrent Event Within Analysis	Assessment of Subjects
Rescue therapy	Composite strategy	Subjects will be considered as treatment failures. The values of the variable of

Intercurrent Event	Strategy to Deal With Intercurrent Event Within Analysis	Assessment of Subjects
		interest collected after the use of rescue therapies will be set to the worst possible value and subject's binary response will be imputed as "Non-responder"
Treatment discontinuation due to lack of efficacy or AE/death related to study drug	Composite strategy	Subjects will be considered as treatment failures. The values of the variable of interest collected after treatment discontinuation due to lack of efficacy or AE/death related to study drug will be set to the worst possible value and subject's binary response will be imputed as "Non-responder"
Treatment discontinuation due to any other reason	Treatment-policy strategy	The values of the variable of interest are used regardless of the occurrence of treatment discontinuation

Table 6 Estimand of Primary Efficacy Endpoint

Primary Efficacy Estimand Description	Estimand Attributes
Estimand 1: In adult hemodialysis patients with chronic kidney disease and associated moderate to severe pruritus, 2 nemolizumab dosing schedules ^[1] compared to placebo by the difference in proportions of responders where response is defined as an improvement from baseline of WI NRS ≥ 4 at Week 12 without use of rescue therapies and without treatment discontinuation due to lack of efficacy or AE/death related to study drug	
Treatment Conditions: initial dose of nemolizumab (60 mg) or placebo at baseline, then nemolizumab (30 mg or 60 mg) or placebo Q4W at Weeks 4 and 8 via subcutaneous injection.
 
Population: adult hemodialysis patients with chronic kidney disease and associated moderate to severe pruritus (will be estimated in the Intent-to-Treat analysis set).
 
Variable: a binary composite response where: Responder is defined as an improvement ≥ 4 in WI NRS from baseline at Week 12 without use of rescue therapies and without treatment discontinuation due to lack of efficacy or AE/death related to study drug. Non-responder is defined as an improvement < 4 in WI NRS from baseline at Week 12 or use of rescue therapies or treatment discontinuation due to lack of efficacy or AE/death related to study drug.
 
Strategies for Intercurrent Events: A composite strategy was chosen for the use of rescue therapies and treatment discontinuation due to lack of efficacy or AE/death related to study drug; in case of use of rescue therapies or treatment discontinuation due to lack of efficacy or AE/death related to study drug, subjects will be considered as treatment failures in the binary composite response. In the case of treatment discontinuation for any other reason, a treatment policy strategy will be used and observed after discontinuation data (if available) will be used.
 
Summary measure: treatment difference of nemolizumab versus placebo in proportions of responders

[1] Dosing schedules compared to placebo Q4W are an initial SC dose of nemolizumab (60 mg) at baseline then either 30 mg or 60 mg Q4W at Week 4 and Week 8.

Summary of estimation is provided in section [Appendix B](#).

Composite binary response variables are defined in a similar manner as in the primary efficacy estimand for the following key secondary estimands where all estimands attributes are as per Estimand 1 except for the variable definition as reported below.

Table 7 Estimands for Key Secondary Efficacy Endpoints

Efficacy Estimand Description	Estimand Attributes
Estimand 2: In adult hemodialysis patients with chronic kidney disease and associated moderate to severe pruritus, 2 nemolizumab dosing schedules ^[1] compared to placebo by the difference in proportions of responders where response is defined as an improvement from baseline of WI NRS ≥ 3 at Week 12 without use of rescue therapies and without treatment discontinuation due to lack of efficacy or AE/death related to study drug	
Treatment Conditions: initial dose of nemolizumab (60 mg) or placebo at baseline, then nemolizumab (30 mg or 60 mg) or placebo Q4W at Weeks 4 and 8 via subcutaneous injection.
 
Population: adult hemodialysis patients with chronic kidney disease and associated moderate to severe pruritus (will be estimated in the Intent-to-Treat analysis set).
 
Variable: a binary composite response where: Responder is defined as an improvement ≥ 3 in WI NRS from baseline at Week 12 without use of rescue therapies and without treatment discontinuation due to lack of efficacy or AE/death related to study drug. Non-responder is defined as an improvement < 3 in WI NRS from baseline at Week 12 or use of rescue therapies or treatment discontinuation due to lack of efficacy or AE/death related to study drug.
 
Strategies for Intercurrent Events: A composite strategy was chosen for the use of rescue therapies and treatment discontinuation due to lack of efficacy or AE/death related to study drug; in case of use of rescue therapies or treatment discontinuation due to lack of efficacy or AE/death related to study drug, subjects will be considered as treatment failures in the binary composite response. In the case of treatment discontinuation for any other reason, a treatment policy strategy will be used and observed after discontinuation data (if available) will be used.
 
Summary measure: treatment difference of nemolizumab versus placebo in proportions of responders

Estimand 3: In adult hemodialysis patients with chronic kidney disease and associated moderate to severe pruritus, 2 nemolizumab dosing schedules ^[1] compared to placebo by the difference in proportions of responders where response is defined as an improvement from baseline of WI NRS ≥ 4 at Week 4 without use of	
Treatment Conditions: initial dose of nemolizumab (60 mg) or placebo at baseline, then nemolizumab (30 mg or 60 mg) or placebo Q4W at Weeks 4 and 8 via subcutaneous injection.
 
Population: adult hemodialysis patients with chronic kidney disease and associated moderate to severe pruritus (will be estimated in the Intent-to-Treat analysis set).
 
Variable: a binary composite response where: Responder is defined as an improvement ≥ 4 in WI NRS from baseline at Week 4 without use of rescue therapies and without treatment discontinuation due to lack of efficacy or AE/death related to study drug. Non-responder is defined as an improvement < 4 in WI NRS from baseline at Week 4 or use of rescue therapies or treatment discontinuation due to lack of efficacy or AE/death related to study drug.

Efficacy Estimand Description	Estimand Attributes
rescue therapies and without treatment discontinuation due to lack of efficacy or AE/death related to study drug	
Strategies for Intercurrent Events: A composite strategy was chosen for the use of rescue therapies and treatment discontinuation due to lack of efficacy or AE/death related to study drug; in case of use of rescue therapies or treatment discontinuation due to lack of efficacy or AE/death related to study drug, subjects will be considered as treatment failures in the binary composite response. In the case of treatment discontinuation for any other reason, a treatment policy strategy will be used and observed after discontinuation data (if available) will be used.

	
Summary measure: treatment difference of nemolizumab versus placebo in proportions of responders


Estimand 4: In adult hemodialysis patients with chronic kidney disease and associated moderate to severe pruritus, 2 nemolizumab dosing schedules^[1] compared to placebo by the difference in proportions of responders where response is defined as an improvement from baseline of SD NRS ≥ 4 at Week 12 without use of rescue therapies and without treatment discontinuation due to lack of efficacy or AE/death related to study drug
	
Treatment Conditions: initial dose of nemolizumab (60 mg) or placebo at baseline, then nemolizumab (30 mg or 60 mg) or placebo Q4W at Weeks 4 and 8 via subcutaneous injection.
 
Population: adult hemodialysis patients with chronic kidney disease and associated moderate to severe pruritus. (will be estimated in the Intent-to-Treat analysis set)
 
Variable: a binary composite response where: Responder is defined as an improvement ≥ 4 in SD NRS from baseline at Week 12 without use of rescue therapies and without treatment discontinuation due to lack of efficacy or AE/death related to study drug. Non-responder is defined as an improvement < 4 in SD NRS from baseline at Week 12 or use of rescue therapies or treatment discontinuation due to lack of efficacy or AE/death related to study drug.

	
Strategies for Intercurrent Events: A composite strategy was chosen for the use of rescue therapies and treatment discontinuation due to lack of efficacy or AE/death related to study drug; in case of use of rescue therapies or treatment discontinuation due to lack of efficacy or AE/death related to study drug, subjects will be considered as treatment failures in the binary composite response. In the case of treatment discontinuation for any other reason, a treatment policy strategy will be used and observed after discontinuation data (if available) will be used.

	
Summary measure: treatment difference of nemolizumab versus placebo in proportions of responders


Estimand 5: In adult hemodialysis patients with chronic kidney disease and associated moderate to severe pruritus, 2 nemolizumab dosing schedules^[1] compared to placebo by the difference in proportions of responders where response is defined as an improvement from baseline of WI NRS ≥ 3 at Week 4 without use of
	
Treatment Conditions: initial dose of nemolizumab (60 mg) or placebo at baseline, then nemolizumab (30 mg or 60 mg) or placebo Q4W at Weeks 4 and 8 via subcutaneous injection.
 
Population: adult hemodialysis patients with chronic kidney disease and associated moderate to severe pruritus (will be estimated in the Intent-to-Treat analysis set).
 
Variable: a binary composite response where: Responder is defined as an improvement ≥ 3 in WI NRS from baseline at Week 4 without use of rescue therapies and without treatment discontinuation due to lack of efficacy or AE/death related to study drug. Non-responder is defined as an improvement < 3 in WI NRS from baseline at Week 4 or use of rescue therapies or treatment discontinuation due to lack of efficacy or AE/death related to study drug.

Efficacy Estimand Description	Estimand Attributes
rescue therapies and without treatment discontinuation due to lack of efficacy or AE/death related to study drug	Strategies for Intercurrent Events: A composite strategy was chosen for the use of rescue therapies and treatment discontinuation due to lack of efficacy or AE/death related to study drug; in case of use of rescue therapies or treatment discontinuation due to lack of efficacy or AE/death related to study drug, subjects will be considered as treatment failures in the binary composite response. In the case of treatment discontinuation for any other reason, a treatment policy strategy will be used and observed after discontinuation data (if available) will be used.
	Summary measure: treatment difference of nemolizumab versus placebo in proportions of responders
Estimand 6: In adult hemodialysis patients with chronic kidney disease and associated moderate to severe pruritus, 2 nemolizumab dosing schedules ^[1] compared to placebo by the difference in proportions of responders where response is defined as an improvement from baseline of SD NRS ≥ 4 at Week 4 without use of rescue therapies and without treatment discontinuation due to lack of efficacy or AE/death related to study drug	Treatment Conditions: initial dose of nemolizumab (60 mg) or placebo at baseline, then nemolizumab (30 mg or 60 mg) or placebo Q4W at Weeks 4 and 8 via subcutaneous injection. Population: adult hemodialysis patients with chronic kidney disease and associated moderate to severe pruritus (will be estimated in the Intent-to-Treat analysis set). Variable: a binary composite response where: Responder is defined as an improvement ≥ 4 in SD NRS from baseline at Week 4 without use of rescue therapies and without treatment discontinuation due to lack of efficacy or AE/death related to study drug. Non-responder is defined as an improvement < 4 in SD NRS from baseline at Week 4 or use of rescue therapies or treatment discontinuation due to lack of efficacy or AE/death related to study drug.
	Strategies for Intercurrent Events: A composite strategy was chosen for the use of rescue therapies and treatment discontinuation due to lack of efficacy or AE/death related to study drug; in case of use of rescue therapies or treatment discontinuation due to lack of efficacy or AE/death related to study drug, subjects will be considered as treatment failures in the binary composite response. In the case of treatment discontinuation for any other reason, a treatment policy strategy will be used and observed after discontinuation data (if available) will be used.
	Summary measure: treatment difference of nemolizumab versus placebo in proportions of responders

[1] Dosing schedules compared to placebo Q4W are an initial SC dose of nemolizumab (60 mg) at baseline then either 30 mg or 60 mg Q4W at Week 4 and Week 8.

6 Subject Disposition

